the various gait modification conditions (study A: 1. baseline; 2. KAM feedback without kinematic instructions, audio and visual feedback; 3. Kinematic feedback without further instructions (toe-out or -in, step width and medial thrust); 4. KAM feedback with additional verbal kinematic instructions about an effective gait pattern that can be sustained in daily life: 5. maintaining the pattern from 4. without any feedback) and during and after the training sessions (study B: 1. baseline; 2. try to replicate the pattern learned in study A without feedback; 3. KAM feedback with kinematic instructions from study A; 4. maintaining the pattern from 3. without feedback; follow-up after 3 and 6 months). Linear mixed models will be used to calculate statistical differences. Secondary parameters will include external knee flexion moment (KFM), and kinematic pattern (joint angles and temporal-spatial parameters) as measured by the GRAIL; pain as measured by the numeric rating scale and will be assessed during the different gait modification patterns (as for the KAM).

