In clinical re-training, there is a focus on a dynamic walking pattern with a spring-like movement in the knee and ankle during loading response for shock absorption. Typically patients tend to adopt a stiff-knee gait pattern with reduced flexion of the knee during stance.

Stance phase flexion requires eccentric control of the quadriceps. Since the quadriceps strength is often reduced in patients with knee osteoarthritis, their gait is adapted to reduce the work required of this muscle group. Clinical therapy focuses on two main areas; firstly improving the co-ordination and timing of the loading and hence re-gaining the stance phase flexion to provide shock absorption and secondly on increasing muscle strength in the quadriceps by walking with bent knees. In clinical practice there is a focus on whole body coordination, including the arm and trunk movements.

In healthy subjects it has been shown that real-time visual feedback on the KAM was most effective in reducing the KAM, in contrast to feedback of a kinematic parameter assumed to influence the KAM [6]. In this study, kinematic feedback was provided on hip internal/ external rotation. By directly controlling the KAM itself, subjects did not show ineffective kinematic compensation strategies that oppose the effect on the KAM. Whether this also applies to KOA patients needs to be investigated and whether patients learn better through implicit learning (i.e. KAM feedback without explicit instructions of gait parameters to change) or explicit instructions on gait parameters remains to be determined. Furthermore, little is known about the effect of feedback training in KOA patients or about the optimal way of using the feedback in clinical practice. Only a few studies have been looked into gait retraining via feedback, using foot progression angles [3;10]. It is unlikely that there will be a "one size fits all" solution to the gait retraining due to the heterogeneous nature of patient cohort. Therefore individual re-training strategies may need to be developed, varying the type and amount of feedback that is presented.

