| Condition | Description | Time (minutes) | Purpose | Recording time (seconds) |
|-----------|--------------------|----------------|----------------------|-----------------------------|
| 0 | Acclimatization to | 3 (max) | To determine the | 0 |
| | treadmill | | average (mean) speed | |
| | | | of walking of the | |

The following protocol will be used in Study A:

| Condition | Description Time (minutes) Purpose | | Purpose | Recording time |
|-----------|---|--|--|--|
| | | | | (seconds) |
| | | | patient for use in further trials. | |
| 1 | Baseline condition- own shoes | 2 | 30 seconds familiarization plus 90 seconds recording time | 90 |
| 2 | Baseline condition- standard shoes | 2 | 30 seconds familiarization plus 90 seconds recording time | 90 |
| 3i | Implicit learning phase- standard shoes with real time visual feedback on KAM | 2 | 30 seconds familiarization plus 90 seconds recording | 90 |
| 3ii | Implicit learning phase- standard shoes with real time audio feedback on KAM | 2 | 30 seconds familiarization plus 90 seconds recording | 90 |
| | | | | |
| 4 | Training phase with explicit instructions | 3 x 2 mins | Feedback on up to 3 kinematic parameters separately 30 seconds familiarisation plus 90 seconds recording | 270 |
| 5 | Measurement- new pattern with feedback | 2 | Measurement of pattern with direct KAM feedback (30 seconds familiarization and 90 seconds recording) | 90 |
| 6 | Measurement- new pattern | 2 | Measurement of pattern without any feedback (30 seconds familiarization and 90 seconds recording) | 90 |
| | | Total walking time: 19.0 minutes maximum (N.B. Regular breaks can be taken as necessary to prevent fatigue). | | Total recording time: 720 seconds =12.0 minutes in 8 individual recordings. |

In stage 3 of the assessment, the subject will be instructed to decrease the KAM. The subjects will therefore apply an individual kinematic strategy to reach this goal [8;43]. Feedback will provide the subject with knowledge of result but not knowledge of performance

so it will up to the individual to devise their own strategy. At this stage no further instructions will be given about kinematic strategies or compensations. This will allow measurement of the implicit motor learning using an external focus of attention [58].

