7. STATISTICAL ANALYSIS

7.1 Primary study parameter(s)

To assess the effect of feedback on external knee adduction moment (KAM) a linear mixed model and repeated measure analysis of variance will be used. Four outcomes parameters will be extracted from the gait cycle, i.e. the KAM peaks at early and late stance with the corresponding KFM values, the KAM during mid-stance, and the impulse (area under curve in %BW*H*sec) [13;43]. In Study A comparison will be made between baseline and gait modification conditions; in Study B the change over time will be calculated for both baseline and replication of learned pattern. The associations between the changes in KAM, KFM, kinematic pattern and pain will be determined.

To identify the factors which predict whether an individual is likely to achieve a good result using the bio-feedback training method, a linear mixed model will again be used.

Statistical significance will be accepted at p-values of less than 0.05. All analyses will be performed using SPSS software, version 21.0 (SPSS, Chicago, IL).

Changes in pain and function over time in study B, as reported using the WOMAC questionnaire and NRS pain scale will also be assessed using a linear mixed model. Patient reported pain and function will be compared during a no-treatment period (immediately following assessment for Study A) and also over time during the intervention period.

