7.2 Secondary study parameter(s)

The secondary outcome measures, external knee flexion moment (KFM), kinematic strategies (i.e. angles of foot, ankle, knee, hip, pelvis and trunk and temporal-spatial parameters) that patients use to decrease the KAM and pain (NRS scale) will also be assessed using a linear mixed model and repeated measure analysis of variance. Linear mixed model will also be used to determine the change of muscle co-contraction, measured with electromyography (EMG) between the different conditions, the adherence, and satisfaction with the program.

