13. APPENDIX A1

The below decision tree is proposed to help the researcher and clinician determine the appropriate feedback instructions for the individual patient based on a) their baseline measures b) their measures during the implicit learning phase (where no instruction will be provided) and c) a priori knowledge (see Table 1). In this way we hope that the subjectivity is removed. Clear instruction will be provided to the patient to ensure that they are aware of how their movements are represented in the on-screen feedback.

If the patient reports pain or discomfort during any of the modifications, then the specific modification thought to be associated with the increased pain level, will be contraindicated for the specific patient. Indications of pain will be recorded on the case record form.

Abbreviations used in the table are explained below.

FPA – foot progression angle, for the purposes of the below table a foot progression angle of greater than 0 (FPA>0) refers to an internally rotated FPA and a foot progression angle of less than 0 (FPA<0) refers to an externally rotated FPA.

KAM- knee adduction moment

KF- knee flexion (referring specifically to the stance phase knee flexion; i.e. during weight bearing.)

SW- step width

TS- trunk sway (note this is included as a variable to monitor, but it will not be used as a variable that is fed back to the patients in order to reduce KAM).

MKT – medial knee thrust. Since we cannot measure knee adduction angle in real time, feedback of this should be the position of the lateral knee marker with respect to the centre of mass in the frontal plane.

Subscript baseline and implicit refer to the data collected in the baseline phase or implicit learning phase.

Subscript patient refers to the average step width in both the baseline and implicit learning phase.

Subscript references refers to normal step width (note this is from healthy individuals walking on the treadmill, but may not be aged matched to the population in this study).

| Gait | IF | AND | AND | THEN | INSTRUCTION TO | INSTRUCTION TO | FEEDBACK EXAMPLE |
|--------------|--------------------------------|----------------------------|----------------------------|----------------------|---------------------------|-------------------------|--|
| modification | | | | | PATIENT (internal | PATIENT (external | (S) |
| | | | | | focus of attention) | focus of attention) | |

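### Foot progression angle is assessed as a pooled signed change although patients may toe in or toe out, so opposite changes partly cancel and the average can miss or understate what patients did

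*Protocol*

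**What the plan says.** Section 7.2 of the Protocol takes as a secondary outcome the "kinematic strategies (i.e. angles of foot, ankle, knee, hip, pelvis and trunk and temporal-spatial parameters) that patients use to decrease the KAM" and states that these "will also be assessed using a linear mixed model and repeated measure analysis of variance". It mentions no direction, no strategy and no count of patients per strategy. Section 7.1 adds that "The associations between the changes in KAM, KFM, kinematic pattern and pain will be determined", without giving the form.

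Other parts of the protocol make the strategy individual:

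- **Implicit phase (Section 5.2, conditions 3i and 3ii).** Patients are told only to lower the KAM. "The subjects will therefore apply an individual kinematic strategy to reach this goal".
- **Kinematic feedback (Summary).** Both foot directions sit in one condition: "Kinematic feedback without further instructions (toe-out or -in, step width and medial thrust").
- **Sign convention (Appendix A1).** An angle above zero is internal rotation, and "a foot progression angle of less than 0 (FPA<0) refers to an externally rotated FPA".
- **Decision table (Appendix A1).** One row covers a rise in foot angle from baseline to the implicit phase and another covers a fall. Both require a lower KAM, and foot-angle modification is then considered appropriate.
- **Rationale (Section 1, Table 1).** Evidence is cited that toe-in and toe-out can each lower some part of the KAM curve.

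**The concern.** One secondary objective of Study A (Section 2) is to evaluate how kinematic patterns change between baseline and modified gait. For foot angle, a mean signed change answers that only if patients move the same way. If some toe in and others toe out, it is the net of two behaviours and describes neither group. Near an even split it approaches zero although every patient changed. With an uneven split it can be significant and still too small. A reader of the results could conclude that foot angle was little used when it was one of the means by which the KAM was lowered.

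**Working it through.** **The plan's own figure.** Section 4.4 gives n = 41 for Study A (two-sided paired t-test, effect size 0.45, alpha 0.05, power 0.80). The noncentral t distribution gives 40.7, so 41, with power 0.803. The figure reproduces, but it is set for the KAM. The protocol gives no figure for kinematic outcomes.

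**Inputs.** n = 41 is from Section 4.4. The toe-in share p is not given for patients, so a range is shown. Assumed: each patient changes foot angle by D = 10 degrees (or 7), with SD s = 4 degrees within a direction. Both values of D lie inside the limit of 15 degrees that Section 5.2 gives as an example.

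**Formulas.** Mean signed change = (2p − 1)D. SD = √(4p(1 − p)D² + s²). Power is that of a two-sided paired t-test.

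Example, p = 0.6, D = 10: mean = 0.2 × 10 = 2; SD = √(0.96 × 100 + 16) = 10.58; noncentrality = 2 × √41 / 10.58 = 1.21; power 22%.

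| Toe-in share | Mean (D = 10) | SD (D = 10) | Power (D = 10) | Power (D = 7) |
|---|---|---|---|---|
| 50% | 0 | 10.77 | 5% | 5% |
| 60% | 2 | 10.58 | 22% | 20% |
| 70% | 4 | 10.00 | 71% | 64% |
| 80% | 6 | 8.94 | 99% | 97% |
| 87.5% | 7.5 | 7.73 | about 100% | about 100% |

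A simulation with other assumed values (5 or 10 degrees, SD 3 or 5) agrees: 5% at 50:50, 28% to 47% at 65:35, 65% to 90% at 75:25, and at least 97% at 87.5:12.5. For 24 patients, the Study B requirement, D = 10 and s = 4 give 5%, 14%, 47% and 88% at shares of 50%, 60%, 70% and 80%.

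**The one split in the document.** Table 1 cites 14 of 16 healthy subjects choosing toe-in (87.5%; exact 95% interval 62% to 98%). It does not say what the other two did. If they toed out, the mean is 0.75 × 10 = 7.5 degrees, 25% too small. If they left foot angle alone, it is 0.875 × 10 = 8.75, 12.5% too small. In neither case is the change missed.

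**Other strategies.** In Appendix A1 step width is only increased and medial thrust has one direction. Patients who do not use them add zeros, which dilutes the mean without reversing it.

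**Association in Section 7.1.** Assumed: n = 41, slope 0.05 %BW*H per degree, residual SD 0.3, changes of 10 degrees.

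- If both directions lower the same KAM parameter, signed foot angle is significant in 6% to 11% of simulated trials at a 50% to 70% toe-in share, against 97% to 98% for the size of the change.
- If the effect is specific to a peak, so that KAM change follows signed angle, power is about 100%.

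**The case against.** **The pooling is inferred.** Section 7.2 names two methods and fixes no model terms. A mixed model can carry strategy or direction, and a statistical analysis plan that is not shown might add them. This stands as a limit: the protocol nowhere says that it averages over all patients. But the usual condition effect of both named methods is that average, and random slopes would describe the spread around it without restoring what has cancelled.

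**Appendix A1 may remove the problem once instructions start.** Its two foot-angle rows, for opposite changes, carry the same instruction: turn the foot towards the treadmill centre. Applied literally, opposite directions would arise mainly in the implicit phase. This stands and narrows the point. The rows still need reconciling with each other and with the Summary, which allows either direction.

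**Stronger readings the documents do not support:**

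- *All kinematic strategies cancel.* This is shown only for foot angle. Table 1 reports a significant group increase in step width of 6 to 7 cm under KAM feedback without instruction.
- *The strategy that worked will be reported as unused.* That needs a split near even. At 14 of 16 the change is detected.
- *The association analysis in Section 7.1 fails in the same way.* That needs both directions to lower the same KAM parameter. Table 1 says toe-in typically lowers only the first peak, and toe-out the second, with the first raised in one healthy-subject study. Section 7.1 extracts both peaks, so signed angle is informative for each. The exposed case is the impulse: Table 1 reports a lower impulse with toe-out and does not exclude the same for toe-in. It also reports a first-peak trend with toe-out in patients, so overlap at that peak is possible too.

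**Conclusion.** The point holds for foot progression angle, mainly in conditions 3i and 3ii. The named analysis yields a net signed change that does not describe what patients did. The loss runs from complete (5% power at an even split) through serious (22% at 60:40) to a 25% understatement with no loss of detection at the 14-of-16 split. These figures assume that all 41 patients change foot angle by a common amount. Patients using another strategy would shrink the mean further. The true split in patients is unknown, so the loss is conditional. The outcome is secondary and the KAM analysis is unaffected. The change is still worth making because it serves a stated objective at little cost.

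**What to change.** 1. **Section 7.2, foot angle.** Beside the pooled mean, report how many patients moved toe-in, toe-out or neither, and the mean change by direction. Keep this descriptive in the implicit phase, where direction is itself a post-baseline response.
2. **Conditions 4 to 6 and Study B.** Reconcile the two foot-angle rows of Appendix A1, record on the case record form the strategy each patient was actually instructed to use, and add that strategy and its interaction with condition or time to the model.
3. **Section 7.1.** Relate foot-angle change to KAM change separately for early peak, late peak and impulse. For impulse, allow a separate slope for each direction.

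One tempting alternative should be avoided: testing absolute change against the difference between the first and second halves of the baseline recording. That yardstick omits variation between trials. Simulated with no true change (assumed between-trial SD 1 to 1.5 degrees, half-trial error SD 0.5 to 1, n = 41), it declared a change in 21% to 100% of trials.

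**Cost.** Analysis wording, one reconciliation in Appendix A1 and one case record form entry; no new visits, patients or gait measurements. The downside is small groups: if the two other subjects in the 14-of-16 split stand for toe-out, 41 × 2/16 gives about 5 toe-out users, so by-direction results should be labelled exploratory.

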7.3 Other study parameters

Changes in postural balance and gait during dual tasking will be also be assessed using a linear mixed model. Changes in physical activity levels between the initial time point and end point of the study, and between the control and intervention group, will be assessed using analysis of variance. As for the primary study parameters, all analyses will be performed using SPSS.

Descriptive statistics will be performed for demographic variables (age, gender, height, weight and duration of (gait) complaints), muscle strength, activity limitations, instability and radiographic Kellgren/Lawrence score.

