Postural balance in patients with knee osteoarthritis is often reduced as a consequence of reduced proprioception at the knee joint [63] [64]. Increased co-contraction of the muscles around the knee may increase the stability of the joint. However increased co-contraction has also been associated with increased joint loading [21]. In early stage osteoarthritis it has been shown that changes in balance may precede changes in gait parameters (including KAM), therefore suggesting that neuro-muscular changes may occur prior to changes in gait [65]. Reduced confidence in the knee and reduced stability may contribute to the higher rate of falls and increased fear of falls in patients with medial knee osteoarthritis [63] [66]. Although the objective of the gait re-training program proposed in this study is not to target balance or stability, quantification of postural balance at the beginning and end of the training phase of this study, alongside self-reported measures of stability may be important in showing neuro-muscular changes.

Activity levels in patients with knee osteoarthritis are often reduced, probably as a consequence of pain and reduced function. In the United States of America, almost two thirds of people with knee osteoarthritis reported walking for less than 90 minutes per week [67]. A systematic review and meta-analysis reported that only a small proportion of people with knee osteoarthritis met physical activity guidelines and recommended daily steps [68]. A second substantial proportion of men and women (40.1% and 56.5%) being classified as inactive. However maintaining physical function is a critical factor for people with osteoarthritis in order to maintain an independent community lifestyle. A study of a large sample of patients (1788 participants) with or at high risk of knee osteoarthritis found that increasing the number of steps taken per day has the effect of increasing protection against functional limitation, as measured by performance and self-report [69]. In addition to protecting against a decline in function other benefits have previously been reported, such as lower prevalence of cardiovascular disease [70]. Benefits of increased activity are well established for the general population and there is also evidence that regular exercise has

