beneficial effects for people with knee osteoarthritis [71]. A novel and individual intervention, such as gait retraining to reduce knee joint loading, may have the effect of increasing the activity levels, either as a consequence of reduced pain levels in the joint, or by increasing motivation. A web-based physical activity intervention showed an increased in physical activity levels in the intervention group compared to the control group 12 months after starting the program [72], providing evidence for the long term benefit of a novel intervention. Objective measurement of physical activity, in the form of number of steps taken per day, is easily captured using a smartphone with built in accelerometer and a freely available application. Therefore, although the main objective of the gait training program is not to increase activity levels, this may be an important side effect of the program and one which can be easily measured using widely available technology.

In summary, there is a large body of evidence to suggest that reduction in the knee adduction moment is beneficial for patients with medial knee osteoarthritis. Furthermore there is evidence to suggest that gait re-training using bio-feedback is beneficial in reducing the KAM. However further research is required in this area to determine the most effective feedback for motor learning in this population. While current research shows that bio-feedback has the immediate effect of reducing the KAM, the longer term effects, including the effect on physical activity level, and the extent of motor learning have not yet been evaluated. Similarly the effect of gait retraining on knee instability and postural balance has not yet been evaluated.

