Note, the patient can take a break at any time during the training/ assessment The total walking time will depend on the week number; see also Figure 2, which presents the faded feedback approach that will be used. The total duration of the training sessions will be increased during the course of the intervention, with a decrease in the feedback time. This approach (termed faded feedback) has been shown to improve motor learning {Winstein, 1990 265 /id} and has been implemented successfully in several studies related to biofeedback for gait retraining including Barrios et al. (2010), Hunt and Takacs (2014) and Shull et al. (2013).

Figure 2: Progression of training and feedback time during the study

In step five, the researcher will provide the patient with home training advice based on the gait retraining methods used in the preceding stages. This may include advice on how to stand up from a chair or how to ascend/ descend stairs. It is important the home training advice complements the advice provided during the gait re-training session.

In addition to the weekly sessions described above, further measurements will be obtained 3 and 6 months after the last training session. This final measurement will consist of both a baseline measurement and replication of the learned pattern, with and without the cognitive dual tasking.

Real-time visual feedback will be provided on the semi-cylindrical screen of the GRAIL. Various types of feedback are available: e.g. bar plot, polar plot, colour change, graph [43] or a number of the actual peak value. Figure 3 shows some examples of feedback that have been used previously in gait modification protocols on the GRAIL. However, other types of visual feedback, such as footsteps indicating desired foot progression angle and/ or step width have been proposed for this study, and have been given a favourable opinion by clinicians. Audio feedback will also be evaluated in Study A.

Figure 3: Examples of different types of real-time visual feedback that can be used on the GRAIL [43].

Knee pain

Knee pain (study A and B) over the past week will be assessed by an 11 point numeric rating scale (NRS; 0 -10), with higher scores representing more pain. Patients will be asked: "What was your pain rating on average over the past week?"

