9.5 End of study report

The investigator will notify the accredited METC of the end of the study within a period of 8 weeks. The end of the study is defined as the last patient's last visit.

In case the study is ended prematurely, the investigator will notify the accredited METC within 15 days, including the reasons for the premature termination.

Within one year after the end of the study, the investigator/sponsor will submit a final study report with the results of the study, including any publications/abstracts of the study, to the accredited METC.

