| | | | the knee | appropriate for this patient | bend your knee and move your knee towards the centre of your body. | your knee and move the marker on your knee towards the centre of your body | with target region – knowledge of performance 2) Target value for medial knee thrust based on MTK _{implicit} shown, with reward when target is reached- knowledge of results |
| Trunk lean/ sway | TS _{implicit} ≫ TS _{baseline} | | | Trunk sway being used excessively to control KAM | Reduce trunk sway | | No feedback given |

| | | Study | Study B | | | | |
|-----------------------|---|-------|---------|----|----|--------------|--|
| | A | | | 1 | | 1 | |
| | | M1 | M1 | M2 | М3 | M4 | |
| | Consent | ✓ | | | | | |
| | Basic demographics | ✓ | | | | | |
| | WOMAC | ✓ | ✓ | ✓ | ✓ | ✓ | |
| | NRS pain over last week | ✓ | ✓ | ✓ | ✓ | ✓ | |
| | Knee instability | ✓ | | | ✓ | ✓ | |
| | Knee confidence | ✓ | | | ✓ | ✓ | |
| | | | | | | | |
| Questionnaires | NRS pain during walking on treadmill | ✓ | 1 | ✓ | ✓ | ✓ | |
| | Feedback on feedback | ✓ | | | | | |
| | Satisfaction with the program | | | | | | |
| | Compliance with the modified | | | ✓ | ✓ | ✓ | |
| | gait pattern | | | | | | |
| | Timed GUG | ✓ | ✓ | | ✓ | \checkmark | |
| | 10m walk test (fast) | ✓ | ✓ | | ✓ | ✓ | |
| Activity/ performance | 10m walk test (comfortable) | ✓ | ✓ | | ✓ | ✓ | |
| lesis | Muscle strength | ✓ | ✓ | | ✓ | ✓ | |
| | | | | | | | |
| | Baseline own shoes | ✓ | ✓ | ✓ | ✓ | ✓ | |
| | | | | | | | |
| | Implicit learning | ✓ | | | | | |
| | Explicit learning 1 | ✓ | | | | | |
| | Explicit learning 2 | ✓ | | | | | |
| Gait and balance | Explicit learning 3 | ✓ | | | | | |
| | Training | | ✓ | ✓ | | | |
| | Retention | ✓ | ✓ | ✓ | | | |
| | Dual tasking- cognitive | | ✓ | ✓ | ✓ | \checkmark | |
| | Dual tasking- physical | | ✓ | ✓ | ✓ | \checkmark | |
| | | | | | | | |

14. APPENDIX A2: Patient measurements at each stage of the patient journey

| Study B | | | | | | | | |
|---------|-----------|----|----|------------|-----|--|--|--|
| T1/ | T2 | Т3 | Τ4 | T 5 | T6/ | | | |

| | M1 | | | | | M2 |
|--|----|---|---|---|---|----|
| NRS pain during last week | ✓ | ✓ | ✓ | ✓ | ✓ | ✓ |
| NRS pain during walking on treadmill | ✓ | ✓ | ✓ | ✓ | ✓ | ✓ |
| Activity levels over last week- step counter | ✓ | ✓ | ✓ | ✓ | ✓ | ✓ |
| | | | | | | |
| Difficulty and "normalness" of learned walking | ✓ | ✓ | ✓ | ✓ | ✓ | ✓ |
| pattern | | | | | | |

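### Section 7.3 analyses activity change up to the study's end point and change in postural balance, but step counts are scheduled only in weeks 1 to 6 and no balance measure is named

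*Protocol*

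**What the plan says.** Section 7.3 contains two analyses of interest. The first is an analysis of variance of "Changes in physical activity levels between the initial time point and end point of the study". The second reads: "Changes in postural balance and gait during dual tasking will be also be assessed using a linear mixed model".

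The only scheduled activity measurement is in the second table of Appendix A2, on the row "Activity levels over last week- step counter". It is ticked at T1/M1, T2, T3, T4, T5 and T6/M2. The first table of Appendix A2, which covers Study A and M1 to M4, has no legible activity row.

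The introduction (Section 1) gives the motivation. It says that "the longer term effects, including the effect on physical activity level" had not yet been evaluated, and makes a similar remark about balance. It also suggests that "quantification of postural balance at the beginning and end of the training" phase may be important.

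For follow-up, Section 5.2 states that "further measurements will be obtained 3 and 6 months after the last training session", and describes the content: "This final measurement will consist of both a baseline measurement and replication of the learned pattern, with and without the cognitive dual tasking".

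**The concern.** An analysis of change needs a measurement at both ends of the interval and a defined outcome. For physical activity, the schedule provides counts during training and none at the visits that close the study for each patient. For postural balance, the analysis section names a construct that the measurement sections never turn into a test or a variable.

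A later statistical analysis plan can define a contrast or choose a variable from recorded data. It cannot supply step counts for visits that have already passed. If the gap is noticed only at analysis, the team will have to pick a different activity contrast and a balance variable after seeing the data, which invites selective reporting. The longer-term activity effect that the introduction raises would also go unmeasured.

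**Working it through.** No sample size, power or error-rate figure is involved, so the check compares the analysis section with the measurement sections.

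**Physical activity**

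1. Visit timing, from the schedule in Section 3: T1/M1 is week 1, T6/M2 is week 6, M3 is week 18 and M4 is week 30.
2. Step-counter ticks, from Appendix A2: weeks 1 to 6, that is 6 of 6 training visits. Legible ticks at the two follow-up visits: 0 of 2.
3. Interval without activity data if the end point is M4: 30 − 6 = 24 weeks.
4. Prose that could fill the gap:
   - Section 3 defines a full assessment as kinematics, kinetics and questionnaires (WOMAC and knee confidence). Activity is not among them.
   - Section 5.1.3 lists the other study parameters. Activity level is not among them.
   - Section 5.2 has no step-count procedure, and its description of the follow-up measurement covers gait conditions and dual tasking only.
5. Meaning of the end point. Section 7.3 does not define it.
   - Reading A, the 6-month visit: Study B runs to 6 months (Sections 2 and 3), and Section 9.5 says "The end of the study is defined as the last patient's last visit". The contrast then has a start value and no end value.
   - Reading B, the end of training: T1 against T6 matches the ticks. The contrast can be computed, but it says nothing about longer-term activity.

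**Baseline week**

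6. The T1 tick asks for activity over the preceding week, so a value before training is scheduled. No section says when the counter is switched on. If it is running by the Study A visit, or the patient's phone already logs steps, the T1 value precedes training. If it is started at T1, the first full week is T1 to T2, after training has begun. The protocol does not say which applies.

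**Postural balance**

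7. Section 5.1 names no balance outcome. Self-reported knee stability is listed, but it is a different construct.
8. Section 5.2 describes no balance test.
9. Appendix A2 has a block labelled for gait and balance. Its legible rows are baseline walking, implicit and explicit learning, training, retention and dual tasking. None is a balance test.
10. Result: a model for change is planned with no stated outcome variable.

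**The case against.** The case on the other side has real weight on five points.

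*The table is an imperfect witness.* The first table of Appendix A2 has blank rows in the text that could be read. It also lacks rows for measurements that are certainly planned: Section 5.2 collects EMG in Study A, in weeks 1 and 6 and at both follow-ups, and no EMG row is legible. Absence from this table alone proves little. That stands as a caution, but the prose of Sections 3, 5.1 and 5.2 is equally silent on step counts at follow-up and on any balance test.

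*The end point may be the end of training.* Section 9.5 is a definition for notifying the ethics committee, not an analysis time point, and the related cognitive-demand outcome is confined to the six training weeks. A reader might infer that the planned activity contrast is unavailable for all 30 patients. The documents support that only under the 6-month reading.

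*A baseline is scheduled.* A reader might also infer that the pre-training activity value is missing. That requires assuming that the counter starts at T1, which the protocol does not say.

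*Balance data may exist.* The wording of Section 7.3 can be read as balance during dual tasking, and dual-task walks are ticked at M1 to M4. So it goes too far to say that the balance analysis has no data. What is missing is a named variable.

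*Importance.* Neither outcome is in the objectives of Section 2. The introduction says that the programme does not target balance and that raising activity is not its main aim. Its remarks on what remains unevaluated describe the literature and are not commitments of this trial. This limits the severity.

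**Conclusion.** The point holds as an inconsistency of minor severity. As written, the schedule supports an activity change from T1 to T6 only. If the end point in Section 7.3 is the 6-month visit, the contrast has no end value and weeks 6 to 30 carry no activity measurement. If it is the end of training, the contrast is computable but the protocol should say so, and the longer-term effect is not addressed. Separately, the balance model has no defined outcome.

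This rests on two assumptions: that no activity or balance row is hidden in the blank rows of Appendix A2, and that no other document schedules these measurements. It is also distinct from the comparison of control and intervention groups in the same sentence of Section 7.3, which does not fit an uncontrolled Study B. Removing that comparison would leave both gaps open. No primary or secondary conclusion depends on either outcome.

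**What to change.** 1. **Activity at follow-up.** Add the step-counter row at M3 and M4 in Appendix A2, and define the Section 7.3 contrast as T1 (the week before training) against M4, with M2 and M3 as intermediate points. If follow-up counts are not wanted, restate the contrast as T1 to T6/M2 and make no claim about longer-term activity.
2. **Baseline week.** State in Section 5.2 that the counter is switched on at least one week before T1, for example at the Study A visit.
3. **Balance.** Delete postural balance from Section 7.3, or name one variable from the gait-lab trials already scheduled at M1 and M2. If a dual-task walk is chosen, first reconcile Section 5.2, which confines dual tasking to weeks 4 to 6, with Appendix A2, which ticks it at M1 in week 1.

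Cost: step-count read-outs at two more visits, a minimum one-week gap between starting the counter and T1, and dependence on patients having a suitable phone. The introduction describes the application as freely available. The alternative in item 1 needs only a change of wording, but gives up the follow-up information. None of this can be recovered reliably once the visits have passed, so it should be settled before patients reach M3.
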